### **STUDY 3**

**Design:** Multicenter, randomized, open clinical trial, without pharmacological intervention, in which the effect of risk stratification in the ED of patients with AHF using the MEESSI-AHF scale prior to the decision to admit or discharge will be evaluated compared to standard medical practice (without risk stratification). The 10 EDs in Study 1 that do not participate in Study 2 will participate in the study, in an attempt to limit contamination, and inclusion will be competitive. Randomization will be performed at the individual level, as the low number of participating EDs and the high heterogeneity of ED organizational models and postal care circuits make this more advisable than randomization by center. Randomization will determine the formation of the two arms of the study (1:1): patients assigned to "usual medical practice" (control group, CG) and those assigned to "risk stratification" (intervention group, IG), which will be done by means of a list provided to each center. The training of emergency professionals and the decision proposal provided by the MEESSI-AHF scale will be the same as in Study 2. The final decision on admission or discharge will depend, as in Study 2, on the emergency physician in charge of the patient, and if this decision differs from that proposed by the stratification, the reason will be stated (the same as in Study 2).

**Study subjects:** All patients diagnosed with AHF in the ED and who meet the inclusion and exclusion criteria mentioned in Study 1 will be eligible.

**Variables:** The independent variables will be the same as in Study 1 with the addition of the center and professional variables. The primary and secondary outcome variables will also be the same as in Study 2.

**Sample size calculation (common with Study 2):** Since the objectives of assessing the effect of the MEESSI-AHF scale on the clinical course of AHF patients in Studies 2 and 3 are the same, the necessary evaluable sample size calculation is the same for both studies, and the principles used are discussed below. On the one hand, the rate of VPR-1 in our setting is around 30% (Llorens et al. *Emergencias*. 2015; 27:11-22). On the other hand, patients discharged from the ED account for 30% of AHFs seen in the ED, and it is estimated that 25% of them will present the event defined by PRV-2. We intend to show that the use of the MEESSI-AHF classification could have a significant impact on a decrease in both PRVs. The 6 centers of Study 2 could assess about 2000 patients in each of the phases of the development of this project. Thus, with 2027 patients, a decrease in 1-year mortality (PRV-1) from 30% to 26% could be seen as statistically significant. As 30% of patients with AHF seen in the ED are discharged, this represents about 600 patients. With 568 patients, a statistically significant decrease in the combined variable (PRV-2) from 25% to 18% can be assessed as statistically significant. With all this, with the inclusion of a little more than 4000 patients (Study 2: 2027 in pre-phase, 2027 in post phase; Study 3: 2027 in GI, 2027 in CG) we could achieve an assessment of a relative decrease as relevant of 13% for PRV-1 and 28% in PRV-2. Calculations were performed using a bilateral type I error of 5% and a statistical power of 80% using the nQuery Advisor program (Ver. 7.0).

**Data collection and analysis (common with Study 2):** The outcome variables in Studies 2 and 3 will be analyzed using logistic or Cox regression models, depending on whether or not it is of interest to contextualize the time of occurrence of the event studied. Specifically, in Study 2, in addition to the application of the MEESSI-AHF scale, the influence of other independent factors of interest in conjunction with the MEESSI-AHF scale will be assessed using multivariate models. In the case of Study 3, since it is a study with randomization by patient (and not stratified by center or professional), it is

proposed that the estimation of the application of MEESSI-AHF should always be adjusted by center and professional in charge of the patient. More exhaustive details of the analysis procedures for the three studies will be reflected in a Statistical Analysis Plan (SAP) agreed with the PI of the project before the closure of the different databases. It will describe in detail both the main analysis population criteria for each study and the statistical analysis of the data. Likewise, the strategy for handling missing data or loss to follow-up of patients will be elaborated.

We would like to point out that the paradigm on which the non-observational part of this research focuses, the use of MEESSI-AHF as an aid in the decision to discharge/admit patients with AHF to the ED, has non-trivial weaknesses. In the case of Study 2, the fact that the two groups (usual clinical practice, pre-phase; and use of the MEESSI-AHF scale; post phase) are not contemporaneous could have an impact on cohort bias, since part of the differences could be due to the temporal effect in the inclusion of patients. In the case of the randomized experimental design, Study 3, the main bias may come from contamination between groups. Given that the patients will be randomized, it is possible that, due to experience of use, there may be professionals who intuit the result that could occur with the MEESSI-AHF scale in patients randomized to routine clinical practice and make the discharge/admission decision in this group with a certain influence of the intervention under study (use of the risk stratification tool). It is therefore proposed that the positive conclusion of the implementation of the MEESSI-AHF scale should be based on obtaining positive results simultaneously in Studies 2 and 3. If not, a post-hoc evaluation of the studies will be necessary to assess possible biases and the impact on the results.

The main termination rule for Study 3, of longer duration than Study 2, would be that in the analysis of PRV-2, which is done at 30 days, a significantly worse evolution is observed in patients in the IG compared to the CG. For this procedure, a specific working group will be created, which will be made up of independent professionals.

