## **METHODOLOGY SECTION**

---

*Design, study subjects, variables, data collection and analysis, and limitations of the study.*

The fulfillment of objectives 1 and 2 will be carried out by means of a single study (STUDY 1) of non-interventional design, with consecutive inclusion of patients in 16 Spanish HEDs, and with a 1-year cohort follow-up. In response to objective 3, two different studies have been designed. The first (STUDY 2) consists of a quasi-experimental before/after study comparing the results obtained in patients with AHF attended in 10 Spanish EDs before and after the implementation of the MEESSEI-AHF scale to stratify the risk of patients with AHF in the ED before the decision to admit or discharge them. The second (STUDY 3) will consist of a multicenter, randomized, open-label, clinical trial comparing the effect of risk stratification of AHF patients in the emergency department using the MEESSEI-AHF scale prior to the decision to admit or discharge the patient.

Ethical aspects: The three studies will be carried out in compliance with the Declaration of Helsinki on research in human beings, the Research Ethics Committees will have been approved and all patients will sign Informed Consent prior to their inclusion in the studies.

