Design: Quasi-experimental before/after study of the effect of implementing the MEESSI-AHF tool to stratify the risk of AHF patients in the ED. Six EDs participating in Study 1 (pre phase) will participate in the present Study 2. After the conclusion of Study 1, the professionals of the 10 EDs will be trained in the use of the MEESSI-AHF scale to stratify risk (post phase). There will be a digital tablet in a centralized location in the ED exclusively dedicated to the calculation of the MEESSI-AHF score. The calculator, which is also available online (<https://semes.org/calculadora-meessi-ahf>) facilitates scoring and classifies the patient into one of four risk categories: low, medium, high or very high. If the patient's classification is "low risk", the system will make the proposal that the patient can be discharged if he or she has shown improvement after the observation period in the emergency department. The ultimate decision, however, will be made by the attending physician. If the patient is not discharged, the reason for not doing so will be classified as: 1) subjective assessment of severity; 2) difficulty of out-of-hospital medical management; 3) lack of out-of-hospital social support; 4) disagreement with the physician's discharge decision, with family or patient refusal; 5) need for admission for an active medical reason not directly related to AHF; and 6) other situations (note). If the patient's classification is "Medium Risk", "High Risk" or "Very High Risk", the system will make the proposal that the patient should be admitted to the hospital. The final decision, however, will be made by the attending physician. If admission is not carried out, the reason for not admitting the patient will be classified, which may be: 1) subjective assessment of non-severity; 2) decision to limit treatment and follow-up at home; 3) disagreement with the physician's decision to admit, with the decision of the family member or the patient to be discharged; and 4) other situations (note).

Study subjects: The inclusion and exclusion criteria will be the same as for Study 1.

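### Open Study 3 assigns patients from a list given to each centre, and the plan describes no step that hides the next assignment until a patient is entered

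*Combined protocol and SAP*

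**What the plan says.** The Study 3 Design paragraph describes a "Multicenter, randomized, open clinical trial, without pharmacological intervention", with 1:1 randomisation of individual patients in 10 emergency departments. On how a patient receives an arm it has one clause: "which will be done by means of a list provided to each center". On recruitment it says that "inclusion will be competitive".

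Four other places bear on the question.

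- The ethics paragraph of the Methodology section says that "all patients will sign Informed Consent prior to their inclusion in the studies".
- The data collection and analysis paragraph shared by Studies 2 and 3 says that Study 3 uses "randomization by patient (and not stratified by center or professional". It concludes that the estimated effect "should always be adjusted by center and professional in charge of the patient".
- The same paragraph defers detail to a later SAP: "It will describe in detail both the main analysis population criteria for each study and the statistical analysis of the data". It adds the handling of missing data and loss to follow-up. That SAP is to be agreed before the databases close.
- Stage 10 of the work plan gives three months to preparing the 10 centres and lists the randomisation procedure among the topics to be reviewed, without describing it.

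The discussion of weaknesses names contamination between arms as the main bias in Study 3. Selection at entry is not discussed.

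**The concern.** Randomisation gives comparable arms only if the person deciding whether to enter a patient cannot know what that patient would receive. In an open trial, staff learn each arm once it is assigned, so the protection has to come from hiding the assignments still to come. A list supplied to the recruiting site, with no stated safeguard, leaves this protection unspecified.

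If the next arm is known, a clinician can hold back, defer or favour a patient according to perceived risk. The arms could then differ in baseline prognosis before the scale has been applied to anyone. The comparison of 1-year mortality across all randomised patients rests on comparable arms. So does the termination rule, which compares the two groups on the 30-day composite. Selection at entry cannot be fully repaired in the analysis.

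**Working it through.** This is mainly a check of the text. The sample size is not in dispute, and the only arithmetic concerns how many allocations depend on the list.

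**How many allocations are involved**

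- Inputs: 2,027 patients per arm (sample size paragraph; Stage 11), 10 centres (Study 3 Design), and 1.5 patients per centre per day on average (Stage 11).
- Total: 2 × 2,027 = 4,054, as Stage 11 states.
- Average per centre: 4,054 / 10 = 405.4. Actual numbers will vary because inclusion is competitive.
- Check on duration: 4,054 / (10 × 1.5) = 270 days, which agrees with the nine months allowed in Stage 11.

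**Does any other provision conceal the next assignment?**

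1. *Consent before inclusion.* This fixes the order of consent and entry. It does not stop the person seeking consent from knowing the next arm when choosing whom to approach.
2. *Stage 10 review of the procedure.* This shows that a procedure is expected to exist, but gives none of its content.
3. *The deferred SAP.* Its stated scope is analysis populations, statistical analysis and missing data, not allocation. Its deadline is database closure, which can fall after enrolment has ended.
4. *Adjustment for centre and professional.* This removes differences between centres and between professionals. If one clinician in one centre enters lower-risk patients when one arm is next and higher-risk patients when the other is next, centre and professional are the same on both sides, so adjustment removes nothing.
5. *Positive results required in both Studies 2 and 3.* Study 2 is a non-randomised before/after comparison. Requiring it to agree does not hide any assignment in Study 3.
6. *The appendix.* The text cites it for the figure comparing the risk scales and for the list of variables, not for allocation.

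None of the six closes the gap.

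**Do per-centre lists fit with unstratified randomisation?**

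Independent lists blocked within each centre would amount to stratification by centre. Simple unblocked lists would not. Nor would one master sequence, blocked overall and cut into centre segments that do not line up with the blocks. The two statements can therefore be reconciled in more than one way, and the plan does not say which applies. It matters here because blocks of a fixed, known size within a centre make some assignments predictable in an open trial, even when the list itself is hidden.

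**The case against.** The strongest reply is that this is silence, not a described fault. A list provided to a centre could be in sealed envelopes or held by someone outside recruitment, and either would fit the wording. The text is a grant application report, and Stage 10 presupposes a procedure to be reviewed. This stands to the extent that a reader might infer that recruiters could see upcoming assignments. The documents do not say so. It does not remove the point: the report calls itself the complete protocol, and the mechanism it states, followed literally, leaves upcoming assignments open to being known.

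Three further inferences are tempting and should not be drawn.

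- *That the entry rate shows selection.* Stage 11 plans 1.5 patients per centre per day, whereas the work plan cites 3 to 5 per centre per day in previous studies. The lower rate simply fits the nine-month window and is not evidence of selective entry.
- *That a false-positive rate can be attached to the gap.* Any such figure needs an assumed baseline imbalance between arms, and the documents supply none.
- *That per-centre lists contradict the absence of stratification, or are compatible with it only if unblocked.* The master-sequence example shows otherwise. This is a request for clarification and is no evidence about concealment.

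It is also fair to say that central allocation is only one of several valid methods. A concealed method with an independent holder of the sequence would serve.

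**Conclusion.** The point holds as follows. Study 3 is open and individually randomised, a list given to each centre is its only stated allocation mechanism, and no described step hides the next assignment until a patient is entered. The method as stated does not prevent recruiters from knowing the next arm, and the planned adjustment would not correct selection that followed from it.

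All 4,054 allocations are affected, about 405 per centre on average. No size or direction of bias is claimed. The conclusion rests on the documents as supplied; a separate written procedure with adequate concealment would answer it. The change should be made because it is cheap and protects the comparison on which the trial depends. It is not a finding that allocation was, or would be, subverted.

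**What to change.** Instead of handing the list to the recruiting sites, release each assignment only after the patient's consent and eligibility have been irrevocably registered. A central, for example web-based, system is preferable. An equivalent concealed method is acceptable if the sequence is held by someone outside recruitment.

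In the protocol, rather than in the later SAP:

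- State who generates the sequence, who holds it, and when the arm is disclosed.
- State whether the per-centre lists are blocked and how they fit with randomisation that is not stratified by centre or professional. If they are blocked within centre, use random block sizes.
- Plan to report baseline MEESSI-AHF risk by arm, calculated retrospectively in controls from variables already collected. This can reveal measured imbalance, but it does not replace concealment.

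The cost is setting up a simple allocation module and a short registration step for each of the 4,054 patients. Sample size and visits do not change.

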discussed in the previous paragraph (11-13), with an ABC COR of 0.836 in the referral cohort and 0.828 in the validation cohort. For a comparison of the main characteristics of the four currently existing scales (STRATIFY, OHFRS, EHMRG and MEESSI-AHF), see the Figure included in the appendix.

The MEESSI-AHF scale proposes a clinical classification into four risk groups: low, medium, high and very high, with all-cause mortalities 30 days after the index event (ED visit) estimated at around 2%, 7%, 15% and 45% for each risk group, respectively. To calculate risk, the scale uses 13 variables available during the patient's first ED visit. This calculation is also facilitated by a freely available online calculator (<http://meessi-ahf.risk.score-calculator-ica-semes.portalsemes.org/>). Furthermore, the development of the scale provides 7 additional mathematical models to the complete model that allow the calculation of risk even in the absence of 3 of the 13 variables that make up the MEESSI-AHF scale (Barthel index of the patient at the ED, troponin and NT-proBNP, in any combination). The MEESSI-AHF scale proposes that those patients classified as low risk would be ideal for the emergency physician to proceed to direct discharge without hospitalization, since the expected mortality in these patients during the following 30 days is very low (around 2% overall).

Subsequently, we revalidated the MEESSI-AHF scale in a new population of 4711 AHF patients from 30 Spanish EDs. Again, the discriminative ability of the scale was very good (ABC ROC of 0.810) and, more importantly, this ability was similar and without significant differences in university and county hospitals, in EDs with different activity loads, and in those EDs that had previously participated in the original development of the scale and those that had not (unpublished data). In the latter, which was a group of 10 EDs that included patients for the first time, the ABC COR was 0.832. In total, therefore, 41 HEDs have already been involved in the MEESSI-AHF scale development project, which represents 12% of the 339 hospitals in the Spanish public health system.

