Ideally, if the decision making made by the emergency physician in current routine clinical practice is correct, the distribution of risk groups in discharged and admitted patients should be markedly different: among the former, low-risk patients should predominate, while among the latter, low-risk patients should be scarce and medium-, high- and very-high-risk patients should predominate. However, this is currently unknown. Secondly, it is important to verify that patients who are classified as low risk by the MEESSI-AHF scale and, as recommended, are discharged, have acceptable adverse event rates, ideally within the recommended standards (19). This has not been proven either, since during the development of the MEESSI-AHF scale only 30-day mortality was used as an adverse event, and furthermore the risk was calculated globally for each risk category, without distinguishing between patients who were discharged and those who were admitted. Recently, an international consensus document has published quality standards to be achieved in the ED for patients with AHF. Specifically, it has proposed a 30-day mortality of less than 2% for patients discharged without hospitalization from the HED with the possibility of maintaining the patient under observation for a period of 24 hours (a circumstance that occurs in most Spanish HEDs), a rate of revisit to the ED for persistence or worsening of AHF during the following 7 days of less than 10% and a rate of revisit to the ED or hospitalization for the same reason at 30 days of less than 20% (19). From the clinical point of view, the low-risk patients on the MEESSI-AHF scale would be those most suitable for discharge directly from the emergency department without hospitalization. And if the results observed in them conform to these proposed standards, this scale could be an ideal instrument

to improve the management of AHF patients in the ED in daily practice based on a better selection of the patient who is in a position to be discharged directly from the ED.

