### **STUDY 1**

Design: Descriptive, multicenter, non-interventional, with consecutive inclusion of patients and 1-year cohort follow-up.

Study Subjects: All patients older than 14 years who consulted in the 16 participating EDs for symptoms and signs compatible with AHF following the Framingham criteria (Ho et al. Circulation 1993; 88:107-15) will be consecutively included and the diagnosis will be verified by determination of natriuretic peptides (BNP or NT-proBNP) (Ponikowski et al. Eur Heart J. 2016;37:2129-200). Failure to confirm clinical suspicion by natriuretic peptide (because it is not determined or is not above the values considered diagnostic) or if the patient presents an episode of AHF in the context of ST-segment elevation acute coronary syndrome (STEMI) will be exclusion criteria, as in most of these cases the patient is transferred to the cardiac hemodynamics unit with minimal ED intervention.

Variables: As independent variables, more than 40 variables will be collected (see appendix) that a priori can potentially be related to the clinical evolution of patients (demographics, personal history, usual chronic treatment at home, baseline functional status and in the acute episode, clinical, analytical and ECG variables of the patient on arrival at the ED, and treatment and management in the ED, including the final destination of the patient after care -discharge/admission-) that are commonly used by the group in their work (Chest 2017; 152: 821-832; JACC Heart Fail 2018; 6:52-62; Eur J Heart Failure 2017; 19:1205-1209), including those necessary for the calculation of the MEESSEI-AHF scale score and patient stratification (Ann Intern Med 2017; 167:698-705). As outcome variables will be collected: 1) cardiovascular and all-cause mortality during the 30 days and year of the index event (ED consultation); 2) ED reconsultation (without admission) for AHF 30 days post-discharge; 3) hospitalization for AHF 30 days post-discharge; 4) all-cause mortality 30 days post-discharge; 5) the combined variable of 2+3+4 30 days post-discharge, and 6) days alive and out of hospital during the 30 days after the index event. Follow-up will be by telephone call to the patient or family member and consultation of hospital and primary care medical records (informed consent will have been collected for this). The adjudication and validation of the event will be carried out

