by the PIs of each center. Given that these are easily objectifiable variables (mortality, admission, emergency consultation), it was not considered necessary for the events to be validated by an external researcher blinded to the MEESSI-AHF application.

Data collection and analysis: Data will be collected on a sheet specifically designed for this purpose, with which the 16 EDs of the participating centers are already familiar due to their previous participation in the EAHFE Registry. To answer Objective 1, the classification variable will be the patient's destination after ED attendance: discharge or admission. In all patients, the MEESSI-AHF score will be calculated retrospectively and they will be classified as low, medium, high or very high risk. The distribution of these risk categories will be compared between both groups (discharge/admission). In addition, the characteristics of low-risk patients in both groups (discharge/admission) will be compared and the propensity for a low-risk patient to be admitted to the hospital will be investigated using multiple logistic regression. The aim is to better understand the factors associated with a likely avoidable hospital admission. On the other hand, medium, high and very high risk patients will be grouped and their characteristics will be compared in both groups (discharge/admission) and the propensity for a medium, high or very high risk patient to be discharged from the emergency department will be assessed by multiple logistic regression. The aim is to better understand the factors associated with probably inappropriate discharges from the ED. For Aim 2, we will compare outcomes obtained in the group of low-risk patients discharged from the ED with published standards: 30-day post-discharge all-cause mortality <2%, 7-day post-discharge ED reconsultation for AHF <10% (this outcome variable will be calculated in this study specifically for this comparison), and 30-day post-discharge ED reconsultation or hospitalization for AHF <20% (Miró et al. Eur J Emerg Med 2017; 24:2-12).

Study limitations: 1) Center selection bias (non-randomized).

## STUDY 2

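### Study 3 names centre and professional as adjustment terms but no patient-level risk covariate; adding the baseline MEESSI-AHF score for 1-year mortality would raise power from about 81% to between 82% and 90%, for an assumed 1-year AUC of 0.60 to 0.80

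*Combined protocol and SAP*

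**What the plan says.** Under Study 3, Data collection and analysis (shared with Study 2), outcomes are to be analysed by logistic or Cox regression. Other independent factors in multivariable models are mentioned specifically for Study 2. For Study 3, randomised by patient without stratification, the text says it is "proposed that the estimation of the application of MEESSI-AHF should always be adjusted by center and professional in charge of the patient". Further detail, including missing data, is left to a SAP to be agreed before the databases close.

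The data for a risk covariate are already planned. Study 3, Variables: "The independent variables will be the same as in Study 1 with the addition of the center and professional variables". The Study 1 list is described as "including those necessary for the calculation of the MEESSEI-AHF scale score and patient stratification". For Study 1 the plan adds: "In all patients, the MEESSI-AHF score will be calculated retrospectively".

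Two statements bear on missing components. The Background says risk can still be calculated without three of the 13 variables ("Barthel index of the patient at the ED, troponin and NT-proBNP, in any combination"). Study 1, Study Subjects, says "the diagnosis will be verified by determination of natriuretic peptides (BNP or NT-proBNP"), so a patient can enter with BNP and no NT-proBNP.

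PRV-1, 1-year all-cause mortality, is measured in all patients whatever their risk category. PRV-2 is measured only in patients discharged directly from the ED.

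**The concern.** The trial tests a score built to predict death in these patients, collects its components in both arms, and has death at one year as a primary outcome. Yet the stated Study 3 model has no term for a patient's baseline risk. Randomisation makes the PRV-1 comparison valid without one, so what is at stake is precision, not bias.

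That precision has some value here. The sample size is set at 80% power, and the protocol says a positive conclusion "should be based on obtaining positive results simultaneously in Studies 2 and 3". A miss in Study 3 alone therefore prevents the pre-specified positive conclusion.

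Two features need care. The trial is open, so use of the calculator in one arm could change which items are measured there, and the reduced model used could then differ by arm. And a covariate chosen after results are known by arm is not credible. The work plan puts the first 30-day analysis of Study 3 in months 19 to 24 and collection of 1-year status in months 31 and 32. A SAP agreed only before database closure could therefore come after outcomes have been seen by arm.

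**Working it through.** **Inputs from the protocol (Study 3, Sample size calculation).** PRV-1 30% versus 26%; 2,027 evaluable patients per arm; two-sided 5%; 80% power.

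**Assumed input.** The AUC of the baseline score for 1-year death. The Background gives 0.836, 0.828 and 0.810 for the scale and says "during the development of the MEESSI-AHF scale only 30-day mortality was used as an adverse event". No 1-year value is given, so the range 0.60 to 0.80 is used.

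**Step 1: reproduce the planned sample size.**

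n = [1.960·√(2·0.28·0.72) + 0.842·√(0.30·0.70 + 0.26·0.74)]² / 0.04² = 1,977 per arm (1,976.7 before rounding).

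With continuity correction: (n/4)·[1 + √(1 + 4/(n·0.04))]² = 2,026.4, rounded up to 2,027. The protocol's figure is reproduced exactly.

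**Step 2: power without the score.**

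- Log odds ratio: ln(0.30/0.70) − ln(0.26/0.74) = 0.1987 in absolute value (odds ratio 0.82).
- Standard error: √[1/(2,027·0.30·0.70) + 1/(2,027·0.26·0.74)] = 0.0701.
- Power: Φ(0.1987/0.0701 − 1.960) = Φ(0.874) = 80.9%. With continuity correction it is 80%.
- Standard error of the risk difference: √[(0.30·0.70 + 0.26·0.74)/2,027] = 1.41 percentage points.

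**Step 3: power with the score.** The model is logit(p) = a + b·x + c·arm, with x a standard normal score. The slope b is set so that the control-arm AUC equals the assumed value. The intercept a and arm effect c are set so that the marginal risks stay at 30% and 26%. The standard error of c comes from the expected Fisher information, and power = Φ(|c|/SE − 1.960). The standardised risk difference has a delta-method standard error. The equivalent increase in sample size is (1.409/SE)² − 1.

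| Assumed 1-year AUC | b per SD | abs(c) | SE of c | Conditional OR | Power | Gain (points) | SE of risk difference (points) | Equivalent extra patients |
|---|---|---|---|---|---|---|---|---|
| 0.60 | 0.36 | 0.204 | 0.0710 | 0.82 | 81.9% | 1.0 | 1.39 | 3% |
| 0.65 | 0.56 | 0.211 | 0.0722 | 0.81 | 83.1% | 2.2 | 1.37 | 6% |
| 0.70 | 0.79 | 0.222 | 0.0741 | 0.80 | 84.9% | 4.0 | 1.33 | 12% |
| 0.75 | 1.05 | 0.238 | 0.0767 | 0.79 | 87.3% | 6.4 | 1.29 | 20% |
| 0.80 | 1.37 | 0.262 | 0.0806 | 0.77 | 90.1% | 9.2 | 1.23 | 32% |

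On the log-odds scale the standard error rises, but the conditional effect moves further from zero, so power increases. On the risk-difference scale the effect stays at 4 points and the standard error falls.

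**Step 4: simulation check.** With ten centre indicators and 3,000 trials per setting, power moves from 80.3% to 80.9%, 82.3% to 83.9%, 81.1% to 84.7%, 80.2% to 86.4% and 81.1% to 90.4%. The gains are 0.6, 1.5, 3.6, 6.2 and 9.4 points, in line with the table.

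**Step 5: Cox model, also allowed by the plan.** With a constant baseline hazard, proportional hazards given the score, censoring at one year and the same marginal risks, power moves from 81.2% to 82.4%, 84.0%, 86.4%, 89.8% and 93.8%.

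**Step 6: both studies positive on PRV-1.** Taking the studies as independent and Study 2 at its 80% design power, 0.809 × 0.80 = 64.7% without the score. With it, the product is 65.5%, 66.5%, 67.9%, 69.8% and 72.1%.

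**The case against.** The strongest reply is that no error has been shown. The sample size reproduces, the unadjusted estimate is valid, and nothing excludes the score. Detail is deferred to a SAP that may well add covariates. All of that stands, which is why this is a suggestion for the SAP. But the present text does choose adjustment terms for Study 3, and a better set can be had from data already planned.

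The size of the gain rests on an AUC the documents do not give. That also stands: the range runs from about 1 to 9 points, and the documents do not locate the value within it. If the reduced model without Barthel, troponin and NT-proBNP is used for everyone, the AUC may be lower and the upper end less likely. The power calculations also leave out the professional term, because the number of professionals is not stated.

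The joint figures mix bases: Study 3 uncorrected at 80.9%, Study 2 at its continuity-corrected 80%. On a single basis the starting value is 0.80² = 64.0% or 0.809² = 65.4%. They also concern PRV-1 alone, so they are not the power of the overall conclusion.

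Finally, the protocol provides a post-hoc evaluation if the two studies are not both positive. That is a further step, but it does not restore the pre-specified positive conclusion.

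One might add that the score is itself the intervention. What is randomised is its use in the disposition decision; the risk it summarises, computed from arrival data, precedes that decision.

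**Conclusion.** The point holds, as an improvement to consider and not as a flaw in validity. Adding the baseline score for PRV-1 raises power from 80.9% to between 81.9% and 90.1% in the logistic model, equivalent to 3% to 32% more patients. This assumes a 1-year AUC of 0.60 to 0.80, a normally distributed score, a constant conditional odds ratio, complete score components and no loss to follow-up. At the low end the gain is negligible. Confidence is medium, because the 1-year AUC is unknown and the professional term is not modelled.

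**What to change.** In the SAP, agreed before any outcome is seen by arm:

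1. For PRV-1, add the continuous baseline MEESSI-AHF linear predictor to the planned centre and professional terms. Compute it from arrival data in the same way in both arms and, in controls, only after the disposition decision.
2. Apply one missing-component rule to all 13 variables, so that the model used does not differ by arm. For example, use the reduced model without Barthel, troponin and NT-proBNP for every patient, and impute any other missing item from baseline data without using arm or outcome.
3. Report a standardised risk difference, so that the result stays on the 30% versus 26% scale. The adjusted odds ratio is conditional and differs from the unadjusted one.
4. Limit this covariate to PRV-1. PRV-2 is measured in patients discharged from the ED, a group the intervention is meant to reshape.

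The cost is some analysis work: scoring controls after disposition and writing the missing-component rule. No new data are required. The reduced model may yield a smaller gain than the table shows.
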